12.4.2 Collection, storage and shipment of technical complaint samples

The investigator must collect the technical complaint sample and notify the monitor **within 5 calendar days** of obtaining the sample at trial site. The monitor must coordinate the shipment to Customer Complaint Center, Novo Nordisk (the address is provided in [Attachment I](#)) and ensure that the sample is sent as soon as possible. A print or copy of the technical complaint form must be sent with the sample.

The investigator must ensure that the technical complaint sample contains the batch number and, if available, the DUN. If the technical complaint sample is unobtainable, the investigator must specify

on the technical complaint form why it is unobtainable. Storage of the technical complaint sample must be done in accordance with the conditions prescribed for the product. The shipment of the technical complaint sample should be done in accordance with the same conditions as for storage (see section [9](#)).

12.5 Pregnancy

12.5.1 Pregnancies in female subjects

Female subjects must be instructed to notify the investigator immediately if they become pregnant during the trial. The investigator must report any pregnancy in subjects who have received trial product(s). Treatment with trial product must be discontinued immediately (see section [6.6.1](#)).

The investigator must follow the pregnancy until the pregnancy outcome and the newborn infant is one month of age. The investigator must report information about the pregnancy, pregnancy outcome, and health of the newborn infant(s), as well as AEs in connection with the pregnancy, and AEs in the foetus and newborn infant.

The following must be collected and reported by the investigator to Novo Nordisk - electronically (e.g. in PDF format), or by fax or courier:

1. Reporting of pregnancy information

Information about the pregnancy and pregnancy outcome/health of the newborn infant(s) has to be reported on Maternal Form 1A and 1B, respectively.

When the pregnancy outcome is abnormal (i.e. congenital anomalies, foetal death including spontaneous abortion and/or any anomalies of the foetus observed at gross examination or during autopsy), and/or when a congenital anomaly is diagnosed within the first month, further information has to be reported for the female subject on Maternal Form 2. In addition, information from the male partner has to be reported on the Paternal Form, after an informed consent has been obtained from the male partner.

Initial reporting and follow-up information must be reported **within 14 calendar days** of the investigator's first knowledge of initial or follow-up information.

2. Reporting of AE information

The investigator has to report AEs in connection with the pregnancy as well as in the foetus and newborn infant(s). The SAEs that must be reported include abnormal outcome, such as foetal death (including spontaneous abortion), and congenital anomalies (including those observed at gross examination or during autopsy of the foetus), as well as other pregnancy complications fulfilling the criteria of an SAE.

Forms and timelines for reporting AEs:

Non-serious AEs:

- Paper AE form* **within 14 calendar days** of the investigator's first knowledge of the initial or follow-up information to the non-serious AE.

SAEs:

- Paper AE form* **within 24 hours** of the investigator's first knowledge of the SAE.
- Paper safety information form **within 5 calendar days** of the investigator's first knowledge of the SAE.
- SAE follow-up information** to the AE form and/or safety information form **within 24 hours** of the investigator's first knowledge of the follow-up information.

- * It must be clearly stated in the AE diagnosis field on the AE form if the event occurred in the subject, foetus or new-born infant.

Any queries or follow-up requests from Novo Nordisk to non-serious AEs, SAEs and pregnancy forms must be responded to by the investigator **within 14 calendar days** from the date of receipt of the request, unless otherwise specified in the follow-up request.

12.5.2 Pregnancies in female partners of male subjects

Male subjects must be instructed to notify the investigator if their female partner becomes pregnant during the trial, except in the screening period. At the last scheduled visit, male subjects must be asked if their female partner has become pregnant.

If a female partner has become pregnant during the trial, the investigator must follow-up on the pregnancy outcome and until the new-born infant is one month of age, irrespective of whether the trial is completed or not. The investigator must ask the male subject and assess, if the pregnancy outcome is normal or abnormal.

When the pregnancy outcome is **normal** this information is recorded in the subject's medical record only, no further information is collected and reported to Novo Nordisk. When the pregnancy outcome is **abnormal** (i.e. congenital anomalies, foetal death including spontaneous abortion and/or any anomalies of the foetus observed at gross examination or during autopsy), the following must be reported by the investigator to Novo Nordisk electronically (e.g. in PDF format) or by fax:

1. Reporting of pregnancy information

Information from the male subject has to be reported on the Paternal Form. Furthermore, information from the female partner (including information about the pregnancy outcome and health status of the infant until the age of one month) has to be reported on the Maternal Forms 1A, 1B and 2, after an informed consent has been obtained from the female partner.

Initial reporting and follow-up information must be reported **within 14 calendar days** of the investigator's first knowledge of initial or follow-up information.

2. Reporting of AE information

The following AEs in the foetus and newborn infant have to be reported:

- Non-serious AEs evaluated as possible/probably related to the father's treatment with the trial product(s).
- SAEs in the foetus and newborn infant - whether or not related to the father's treatment with the trial product(s). This includes an abnormal outcome - such as foetal death (including spontaneous abortion) and congenital anomalies (including those observed at gross examination or during autopsy of the foetus).

Forms and timelines for reporting AEs:

Please see section [12.5.1](#), point 2, "Forms and timelines for reporting AEs:".

Any queries or follow-up requests from Novo Nordisk to non-serious AEs, SAEs and pregnancy forms must be responded to by the investigator **within 14 calendar days** from the date of receipt of the request, unless otherwise specified in the follow-up request.

12.6 Precautions and/or overdose

At present, there is no experience of overdose with NNC0195-0092 in humans. In NN8640-3915 healthy male volunteers were dosed with up to 0.32 mg NNC0195-0092/kg (SD up to 0.32 mg/kg and MD up to 0.24 mg/kg). All adverse events were mild or moderate and primarily observed at the highest dose levels. Most common adverse events were: headache, peripheral oedema, joint pain, muscle pain and increase in blood sugar and insulin levels. In a recent trial in adults with GHD receiving multiple doses of the drug, the same safety profile of adverse events were registered. These adverse events are similar to those observed for existing growth hormone products on the market. For further details please refer to IB¹⁷.

Any overdose should be reported as an AE, with or without clinical manifestations. Overdoses are considered medication errors and thus MESIs.

12.7 Committees related to safety

12.7.1 Novo Nordisk safety committee

Novo Nordisk has constituted an internal NNC0195-0092 safety committee to perform ongoing safety surveillance according to the NNC0195-0092 safety committee guideline. The NNC0195-0092 safety committee may recommend unblinding of any data for further analysis, and in this case an independent ad hoc group will be established in order to maintain the blinding of the trial personnel.

13 Case report forms

Novo Nordisk will provide a system for the electronic case report forms (eCRF). This system and support services to the system will be supplied by a vendor.

Ensure that all relevant questions are answered, and that no empty data field exists. If a test or an assessment has not been done and will not be available, or if the question is irrelevant (e.g. is not applicable), indicate this according to the data entry instructions.

The following will be provided as paper CRFs:

- Pregnancy forms (including AE forms and SIF in relation to pregnancy)

In addition paper AE forms, safety information forms and technical complaint forms will be provided. These must be used when access to the eCRF is revoked.

On the paper CRF forms print legibly, using a ballpoint pen. Ensure that all questions are answered, and that no empty data blocks exist. Ensure that no information is recorded outside the data blocks. If a test/assessment has not been done and will not be available, indicate this by writing "ND" (not done) in the appropriate answer field in the CRF. If the question is irrelevant (e.g. is not applicable) indicate this by writing "NA" (not applicable) in the appropriate answer field. Further guidance can be obtained from the instructions in the CRF.

The investigator must ensure that all information is consistent with the source documentation. By electronically signing the case book in the eCRF, the investigator confirms that the information in the eCRF and related forms is complete and correct.

13.1 Corrections to case report forms

Corrections to the CRF data may be made by the investigator or the investigator's authorised staff. An audit trail will be maintained in the CRF application containing as a minimum: the old and the new data, identification of the person entering the data, date and time of the entry and reason for the correction. If corrections are made by the investigator's authorised staff after the date the investigator has signed the case book, the case book must be signed and dated again by the investigator.

13.2 Case report form flow

The investigator must ensure that data is recorded in the eCRF as soon as possible, preferably within 5 days after the visit. Once data has been entered, it will be available to Novo Nordisk for data verification and validation purposes.

Site specific eCRF data (in an electronic readable format) will be provided to the trial site before access to the eCRF is revoked. This data must be retained at the trial site.

14 Monitoring procedures

During the course of the trial, the monitor will visit the trial site to ensure that the protocol is adhered to, that all issues have been recorded, to perform source data verification and to monitor drug and ecap accountability. The first monitoring visit will be performed as soon as possible after FSFV and no later than 4 weeks after. The monitoring visit intervals will depend on the outcome of the remote monitoring of the CRFs, the trial site's recruitment rate and the compliance of the trial site with the protocol and GCP, but will not exceed 12 weeks. If no subjects are enrolled at a site the monitoring visit interval will not exceed 18 weeks.

The monitor must be given direct access to source documents (original documents, data and records). Direct access includes permission to examine, analyse, verify and reproduce any record(s) and report(s) that are important to the evaluation of the trial. If the electronic medical record does not have a visible audit trail, the investigator must provide the monitor with signed and dated printouts. In addition the relevant trial site staff should be available for discussions at monitoring visits and between monitoring visits (e.g. by telephone).

All data must be verifiable in source documentation other than the CRF. The only exceptions are race and ethnicity and the unique number of ecaps dispensed to a subject which can be recorded directly in the eCRF. History of GHD and diagnosis must be source data verifiable and reasonable efforts must be put into acquiring medical records from primary physicians or other hospitals or departments.

For all data recorded the source document must be defined in a source document agreement at each trial site. There must only be one source defined at any time for any data element.

Source data generated by the trial site can be corrected by another person than the person entering the source data if accepted by local regulations; any correction must be explained, signed and dated by the person making the correction.

The monitor will ensure that the CRFs are completed, diaries entered in the eCRF and that paper PROs are collected. The original diaries and PROs must not be removed from the trial site.

Monitors must review the subject's medical records and other source data (e.g. the diaries and PROs) to ensure consistency and/or identify omissions compared to the CRF. If discrepancies are found, the investigator must be questioned about these.

The monitor will collect CRF pages and other trial related forms containing data from screening failures. The existence of the subject and the reason for screening failure must be source data verifiable.

A follow-up letter (paper or electronic) will be sent to the investigator following each monitoring visit addressing any action to be taken.

14.1 Titration surveillance

Surveillance of trial product titration will be performed centrally by an independent Novo Nordisk Titration Group not otherwise involved in the conduct of the trial. Surveillance will be performed on an on-going basis throughout both the main and extension trial until all subjects have completed dose titration. The titration group reviews the information provided by the investigator in case of deviations and follows up accordingly. The titration group will be blinded towards treatment allocation.

15 Data management

Data management is the responsibility of Novo Nordisk.

Appropriate measures, including encryption of data files containing person identifiable data, will be used to ensure confidentiality of subject data, when they are transmitted over open networks.

Data from central laboratories will be transferred electronically from the laboratory performing the analyses. In cases where data is transferred via non-secure electronic networks, data will be encrypted during transfer.

The subject and any biological material obtained from the subject will be identified by subject number and trial identification number. Appropriate measures such as encryption or leaving out certain identifiers will be enforced to protect the identity of subjects in all presentations and publications as required by local, regional and national requirements.

Two partial database locks are planned to be done during the trial (facilitating interim safety reporting and analysis of main trial period data, respectively) as well as a database lock after the extension period of the trial is completed. For details please refer to section [17.5](#).

16 Computerised systems

Novo Nordisk will capture and process clinical data using computerised systems that are described in Novo Nordisk Standard Operating Procedures and IT architecture documentation. The use and control of these systems are documented.

Investigators working on the trial may use their own electronic systems to capture source data.

17 Statistical considerations

If necessary, a statistical analysis plan (SAP) may be written in addition to the protocol, including a more technical and detailed elaboration of the statistical analyses. The SAP will be finalised before database lock.

Biostatistics, Novo Nordisk, will be responsible for the statistical analyses.

All statistical tests conducted will be two sided on the 5% level. Region is defined as a factor with 2 levels: Japan and all other countries.

17.1 Sample size calculation

Under the assumption of a true mean difference of 2.5% between NNC0195-0092 and placebo and a standard deviation (SD) of 4.5% for the primary endpoint and based on a two-sided, two-sample t-test with a significance level of 5% and a 2:1 randomisation ratio between NNC0195-0092 and placebo, 104 subjects in the NNC0195-0092 treated group and 52 subjects in the placebo treated group completing the main trial should ensure 90% power for detecting a difference between NNC0195-0092 and placebo. The assumptions of a true mean difference of 2.5% between active treatment and placebo and a SD of 4.5% is slightly conservative to what is observed in similar trials. In a secondary comparison of the primary endpoint, it will be possible to expect with probability 0.87 that half the length of the 95% confidence interval (CI) constructed for the difference between NNC0195-0092 and Norditropin[®] FlexPro[®] will be at most 1.3% if additional 104 subjects are enrolled in the Norditropin[®] FlexPro[®] treated group, resulting in a total of 260 subjects to be included in the trial. Expecting at most 7% drop-out from the trial, 280 subjects should be included in the trial.

Simulations (10000 samples, analysis based on multiple imputation technique as described in section [17.3](#)) under the the assumption of a drop-out rate of 7% and an additional assumption that 50% of the subjects who do not complete the main trial contribute to the primary analysis with post-randomisation DXA data, gives 89% power for detecting a difference between NNC0195-0092 and placebo with 112 subjects in the NNC0195-0092 treated group and 56 subjects in the placebo treated group. If the assumptions are changed to a drop-out rate of 15% and all subjects who do not complete the main trial will have no post-randomisation DXA data, then simulations gives 78% power for detecting a difference between NNC0195-0092 and placebo.

17.2 Definition of analysis sets

Two analysis sets are defined.

The full analysis set (FAS) used for evaluations of efficacy endpoints includes all randomised subjects that received at least one dose of randomised treatment. Only in exceptional cases may subjects be excluded from the FAS. Subjects will be analysed “as randomised”.

The safety analysis set (SAS) used for evaluations of safety endpoints includes all randomised subjects that received at least one dose of randomised treatment. Subjects will be analysed “as treated”.

A partial database lock of all data obtained up to Week 35 is planned to take place shortly after the last dosed subject has passed the assessments of Week 35 (main trial). The subjects or observations to be excluded, and the reasons for their exclusion must be documented and signed by those responsible before database lock. The subjects and observations excluded from analysis sets, and the reason for this, will be described in the clinical trial report.

In the extension trial period the data for the efficacy analysis will be analysed using the randomized treatment from the start of the main trial period in combination with the allocated/randomized treatment in the extension phase. There will thus be four groups in the extension trial: NNC0195-0092 /NNC0195-0092, placebo/NNC0195-0092, Norditropin[®] FlexPro[®]/Norditropin[®] FlexPro[®] and Norditropin[®] FlexPro[®]/NNC0195-0092. Subjects not participating in the extension trial will be included based on their main trial randomization with a special case for Norditropin[®] FlexPro[®] subjects who will be included in the Norditropin[®] FlexPro[®] /Norditropin[®] FlexPro[®] group. For the safety endpoints the actual treatment (main trial period) in combination with the actual treatment (extension trial period) will be used for the analysis.

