5.1 Type of trial

This is a multicentre, multinational, randomised, parallel-group, placebo-controlled (double blind) and active-controlled (open) trial to compare the efficacy and safety of once weekly dosing of NNC0195-0092 with once weekly dosing of placebo and daily dosing of Norditropin® FlexPro® in adults with GHD during a 35-week period, with a 53-week extension period.

[figure not shown]

Figure 5-1 Trial design

Two hundred and eighty (280) subjects will be randomised in a 2:2:1 ratio to receive NNC0195-0092, Norditropin® FlexPro® or placebo during a 35-week period (8 weeks of titration, followed by 26 weeks of treatment and 1 week of washout). The randomisation will be stratified according to two region levels (Japan and all other countries), sex (male and female) and diabetic status (diagnosed with diabetes mellitus vs. not diagnosed with diabetes mellitus). All subjects completing the 35-week period will continue their active treatment with NNC0195-0092 weekly injection or Norditropin® FlexPro® daily injection in a non-placebo-controlled design for an additional 53-week extension period (8 weeks of titration, followed by 44 weeks of treatment and 1 week of washout). Placebo subjects will be switched to NNC0195-0092 treatment and Norditropin® FlexPro® subjects will be re-randomised 1:1 to NNC0195-0092 or Norditropin® FlexPro® within the same strata as used for the first randomisation. During the extension period subjects will be seen on a regular basis for adverse events, safety laboratory measurements, and efficacy.

The trial flow is depicted in [Table 2-1](#) (main trial period) and [Table 2-2](#) (extension period).

A blinded interim reporting of all safety parameters as described in sections [8.5](#) and [17.5](#) is planned to be done when 50 subjects randomised to NNC0195-0092 have completed the main trial. Data for

all subjects up to week 35 (see [Table 2-1](#)) who have completed the main trial at this time will be included.

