12.2 Reporting of adverse events

All events meeting the definition of an AE must be collected and reported. This includes events from the first trial-related activity after the subject has signed the informed consent until the end of the post-treatment follow-up period (i.e. Visit 29 or Visit 15 if a subject does not wish to participate in the extension part of the trial). The events must be recorded in the applicable eCRF forms in a timely manner, see timelines below and [Figure 12-1](#).

During each contact with the trial site staff, the subject must be asked about AEs and technical complaints, for example by asking: "Have you experienced any problems since the last contact?"

All AEs, either observed by the investigator or subject, must be reported by the investigator and evaluated. Novo Nordisk assessment of expectedness is performed according to the following reference documents: IB¹⁷ and the Company Core Data Sheet (CCDS), current version or updates hereof.

All AEs must be recorded by the investigator on an AE form. The investigator should report the diagnosis, if available. If no diagnosis is available, the investigator should record each sign and symptom as individual AEs using separate AE forms.

For SAEs, a safety information form (SIF) must be completed in addition to the AE form. If several symptoms or diagnoses occur as part of the same clinical picture, one SIF can be used to describe all the SAEs.

MESIs, regardless of seriousness, must be reported using both the AE form and the SIF.

The AE form for a non-serious AE should be signed when the event is resolved or at the end of the trial.

Timelines for initial reporting of AEs:

The investigator must complete the following forms in the eCRF within the specified timelines:

- **SAEs:** The AE form **within 24 hours** and the SIF **within 5 calendar** days of the investigator's first knowledge of the SAE.

Both forms must be signed within 7 calendar days from the date the information was entered in the eCRF.

- **Non-serious AE fulfilling the MESI criteria:** The AE form, and SIF **within 14 calendar days** of the investigator's first knowledge of the event.

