17.3 Primary endpoint

The primary endpoint is change from baseline (randomisation) to end of main trial period (Week 34) in truncal fat percentage.

The primary objective of the trial is to demonstrate the efficacy of once weekly dosing of NNC0195-0092 after 34 weeks of treatment in adults with GHD and the primary analysis of the primary endpoint will be the primary tool for achieving this. Body composition is measured by DXA and truncal fat percentage is defined as 100 times truncal fat mass (kg) divided by the sum of truncal fat mass (kg) and truncal lean body mass (kg).

Truncal fat percentage as a function of time since baseline is expected to be monotone if the subject stays on the randomised treatment in the main trial period. Based on this assumption, the primary analysis of the primary endpoint will be conducted using a multiple imputation technique where the trajectory after a withdrawn subject’s last observation is imputed based on data from the placebo arm, thus mimicking an intention to treat (ITT) scenario where withdrawn subjects are assumed to be switched to no treatment (placebo) after withdrawal. For each of 100 copies of the dataset (seed=34247), an analysis of covariance (ANCOVA) model with GHD onset type (adult or child), sex, region, DM (diabetic status) and sex by region by DM interaction as factors and baseline truncal fat (%) as a covariate. is fitted to the change in truncal fat percentage from baseline to 34 weeks data for the placebo group only. The estimated parameters, and their variances, from this model are used to impute missing values at 34 weeks for subjects in all treatment groups, based on

their sex, region, DM, GHD onset type and baseline truncal fat values. If a truncal fat assessment for a subject has been performed after baseline at intermediate time t (e.g. in connection with the end-of-trial visit for withdrawn subjects, section 8.2) this information will be combined with the time-normalized model based estimate so that the final imputed value for the subject is a sum of the observed value at time t and the model based estimated change multiplied by (34 weeks-t)/(34 weeks) minus the baseline value.

For each of the complete data sets, the change from baseline to 34 weeks is analysed using an ANCOVA model with treatment, GHD onset type, sex, region, DM and sex by region by DM interaction as factors and the baseline truncal fat value as a covariate.

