The data will be analysed using descriptive statistics. This analysis will be supplemented with exploratory analysis on changes from baseline to end of extension period (Week 87) data based on MMRM analysis models similar to the main trial period data analysis, where NNC0195-0092/NNC0195-0092 and Norditropin[®] FlexPro[®]/Norditropin[®] FlexPro[®] arms will be compared. For TSQM scores the analysis will be made on Week 87 data and not change from baseline data. The interpretation of these analysis results should take into account the added complications inherent in analysing data from an extension period, including selection bias.

The NNC0195-0092 and hGH serum concentration data will be analysed using descriptive statistics. The data will also be used in the population PK analysis described in section [17.6](#).

Compliance with treatment will be evaluated based on time stamps from the ecaps in the extension period and diary data in the main trial period and the extension period. The data will be analysed using descriptive statistics.

A Kaplan-Meier plot of the time-to-withdrawal will be presented by treatment arm and the implication on the efficacy analysis of any marked differences will be commented upon in the clinical trial report.

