Data will be analysed using descriptive statistics and will support the future phase 3 trial programme in children with GHD (regulatory requirement). As the safety data will be reported in a blinded manner (once weekly arms combined (NNC0195-0092 or placebo) versus Norditropin[®] FlexPro[®]) no impact is expected on the remainder of the trial.

Second partial DBL (main trial)

Data for all subjects up to and including V15 who have completed or discontinued the main trial will be included in a partial database lock (second partial database lock of trial data). After the second partial DBL the sponsor will become unblinded while the subjects and site personnel will remain blinded regarding the NNC0195-0092 versus Placebo allocation during the main period.

Final DBL (extension)

The extension trial is open-label after the main trial period and the data from the extension period will support the secondary objective of evaluating the efficacy and safety of NNC0195-0092 for up to 86 weeks of treatment in adults with GHD, but will not contribute with confirmatory results.

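### Minor: placing every Norditropin subject who skips the extension in Norditropin/Norditropin, while continuers are split 1:1, nearly doubles the non-continuer share in that group relative to its Week 87 comparator

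*Protocol*

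**What the plan says.** Section 5.1 states that after the main period Norditropin "subjects will be re-randomised 1:1 to NNC0195-0092 or" Norditropin, "within the same strata as used for the first randomisation". Those strata are region, sex and diabetic status.

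Section 17.2 then sets up four groups for the extension efficacy analysis. On those who do not enter the extension it says: "Subjects not participating in the extension trial will be included based on their main trial randomization with a special case for" Norditropin subjects, who are all placed in Norditropin/Norditropin. None goes to Norditropin/NNC0195-0092.

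Section 17.4.1.1 plans descriptive statistics for the extension, supplemented by "exploratory analysis on changes from baseline to end of extension period (Week 87) data based on MMRM analysis models" like those of the main period, comparing NNC0195-0092/NNC0195-0092 with Norditropin/Norditropin. It adds a general caution about selection bias. Section 17.5 says the extension data "will not contribute with confirmatory results".

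Neither the amendments provided nor SAP version 2.0 changes the grouping rule. The SAP's analysis updates cover only TRIM-AGHD and body weight.

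**The concern.** The two groups compared at Week 87 are built differently. One is a complete randomised arm. The other is a random half of an arm's continuers plus all of that arm's non-continuers, so non-continuers are over-represented in it even when both arms lose subjects at the same rate.

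Non-continuers have no Week 87 value, but that does not keep them out of the model. The main-period MMRMs exclude only subjects with no post-randomisation data. A non-continuer with earlier visits therefore enters and moves the Week 87 estimate through the covariance between visits. If non-continuers respond less than continuers, Norditropin/Norditropin looks slightly worse than it should; if they respond more, slightly better.

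Section 5.2 gives continued comparison of the two active treatments as one reason for re-randomising Norditropin subjects, so this is the contrast the extension design is meant to support.

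**Working it through.** **Inputs from the documents**
- Arm sizes 112 / 112 / 56 (section 5.3); 260 of 280 expected to complete the main period (section 6.1).
- Drop-out of at most 7%, SD 4.5 points, assumed effect against placebo 2.5 points (section 17.1).
- Simulation assumption in section 17.1 that "50% of the subjects who do not complete the main trial contribute to the primary analysis with post-randomisation DXA data".

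**The plan's own figures.** An exact two-sided t-test with 104 versus 52 subjects, difference 2.5 and SD 4.5 gives power 0.902, against the stated 90%. Inflating for drop-out, 260/0.93 = 279.6, so 280. Both reproduce. Hence 104 of 112 complete in each active arm and 8 do not.

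**Headcount shares,** with c continuers and x non-continuers per arm, if all completers continue:
- Norditropin/Norditropin: x/(c/2 + x) = 8/(52 + 8) = 8/60 = 13.3%.
- NNC0195-0092/NNC0195-0092: x/(c + x) = 8/112 = 7.1%.
- Difference: 0.062.
- At the 15% drop-out also considered in section 17.1 (c = 95.2, x = 16.8): 16.8/64.4 = 26.1% versus 15.0%.

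Section 12.2 foresees an adverse-event cut-off at "Visit 15 if a subject does not wish to participate in the extension part of the trial", so some completers may decline. The plan gives no rate for them; any such refusals would raise both shares.

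**Shares in a DXA model.** If half of the drop-outs have a usable scan: 4/(52 + 4) = 4/56 = 7.1% versus 4/(104 + 4) = 4/108 = 3.7%, a difference of 0.034.

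Whether those scans enter is not stated. For the Week 34 analysis, section 17.3 treats a withdrawal scan as an interim value ("If a truncal fat assessment for a subject has been performed after baseline at intermediate time t"), but nothing says how it is used in the Week 87 MMRM. If it is not used, the DXA shift from drop-outs is zero.

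**Shift in the Week 87 contrast** = difference in shares × gap × slope. Assumptions, not document figures: non-continuers respond 1 or 2 points less, the slope of Week 87 on Week 34 is 0.5 to 0.8, and withdrawal scans enter as Week 34.

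| Gap | 4 scans per arm | 8 scans per arm |
|---|---|---|
| 2 points | 0.034 to 0.055 | 0.062 to 0.099 |
| 1 point | 0.017 to 0.028 | 0.031 to 0.050 |

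**Standard error.** Per arm, Var = SD²[(1 − r²)/n87 + r²/n34]. With 4 scans, n87 is 104 and 52; n34 is 108 and 56 as planned, or 108 and 108 if all Norditropin subjects form one arm up to re-randomisation.
- r = 0.5: planned √{20.25 × [0.75 × (1/104 + 1/52) + 0.25 × (1/108 + 1/56)]} = 0.759; one arm 0.729 (−3.9%).
- r = 0.8: planned 0.750; one arm 0.671 (−10.5%).

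**Simulation check** (two visits, monotone missing data, SD 4.5, gap 2, no true difference, 60,000 runs per scenario, Monte Carlo error about 0.003). Entries are shift / SE / mean squared error. A negative shift favours NNC0195-0092.

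| Scans, r | Planned rule | Half weight for Norditropin non-continuers | One Norditropin arm |
|---|---|---|---|
| 4, 0.5 | −0.037 / 0.757 / 0.574 | −0.003 / 0.758 / 0.574 | −0.003 / 0.728 / 0.531 |
| 4, 0.8 | −0.057 / 0.747 / 0.561 | −0.002 / 0.750 / 0.562 | −0.002 / 0.670 / 0.449 |
| 8, 0.5 | −0.069 / 0.752 / 0.571 | −0.007 / 0.754 / 0.569 | −0.005 / 0.727 / 0.528 |
| 8, 0.8 | −0.099 / 0.739 / 0.556 | 0.000 / 0.744 / 0.553 | +0.002 / 0.667 / 0.445 |

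The one-arm rule also has the lowest mean squared error in all four cases at a gap of 1 point.

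**The case against.** The best defence is that the effect is negligible. The largest simulated shift, 0.099 against an SE of 0.739, is 0.13 SE, which would raise a two-sided 5% error rate only to about 5.2%. Half-weighting removes the imbalance alone and leaves the mean squared error almost unchanged. The 2-point gap is also demanding: it is the top of the 0 to 2% range in the section 17.3 sensitivity analysis and 80% of the assumed drug effect (2/2.5). All of this stands, and it is why the point is minor.

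It is also fair that the precision gain is a separate matter. It comes from using main-period data of subjects later switched to NNC0195-0092, and would arise without any imbalance. It shows that the correction costs no precision; it is not evidence that the rule is wrong.

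Two other arguments carry less weight. Section 17.4.1.1 already warns of selection bias and adds a Kaplan-Meier plot of time to withdrawal by arm. But equal withdrawal in both arms, which such a plot would show as no difference, still produces 13.3% versus 7.1%, because the grouping rule creates the imbalance. The rule is also deliberate, matches the treatment these subjects were assigned, and keeps the full analysis set. The alternative keeps the full analysis set too.

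**Conclusion.** The concern holds and is minor. The headcount imbalance, 13.3% versus 7.1%, follows directly from the planned numbers, given that all completers continue. Its effect is conditional: about 0.03 to 0.10 truncal-fat points at a 2-point gap and correlations of 0.5 to 0.8, half that at 1 point, and none if non-continuers resemble continuers. For DXA endpoints it also requires that withdrawal scans enter the model. Endpoints with several main-period visits (IGF-I, patient-reported outcomes, body weight) do not depend on that and can carry up to the headcount shares; no shift was computed for them.

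The contrast is exploratory. The primary, Week 34 and as-treated safety analyses are unaffected. The point is worth correcting because the imbalance is avoidable at almost no cost.

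**What to change.** In the Week 87 MMRM, code all subjects first randomised to Norditropin as one Norditropin arm for main-period visits, up to Visit 15 and before the first extension dose. Omit the later visits of those re-randomised to NNC0195-0092. Those visits are then missing by random design within sex, region and diabetic-status strata, which are already in the model. Non-continuers become 8/112 in both arms by headcount, and no subject leaves the full analysis set. Keep the four groups for the descriptive extension tables. State whether, and at which visit, withdrawal DXA scans enter this model.

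An acceptable alternative is to keep the planned grouping and give Norditropin non-continuers weight 1/2 with a robust variance. By headcount this gives 4/56 = 7.1%, equal to the comparator. It removes the bias at a very small loss of precision.

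The cost is SAP wording and a little programming, with no new data and no change in trial conduct. With the one-arm rule the SE falls by about 3 to 10% under the assumed correlations.
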